4.1.1 Inclusion Criteria

Dose Escalation, Maintenance Arm A

- Patients with ES-SCLC who have completed 4-6 cycles of carboplatin and etoposide induction chemotherapy, with or without *atezolizumab*, as their first-line therapy for extensive-stage disease and have responded (CR or PR) or have SD are eligible for the maintenance arm of the study.
- All side effects attributed to prior anti-cancer therapy must have resolved to Grade 1 or baseline.
- A maximum of 8 weeks (56 days) is allowed between last chemotherapy dose (Cycle 4, Day 3) given in induction and the start of maintenance therapy.

Dose Escalation, Induction Arm B

- Patients with no prior systemic treatment for ES-SCLC are eligible for this study.
- ANC \geq 1,500 cells/µL without granulocyte colony-stimulating factor support

Dose Expansion, Maintenance-Only

• Patients with ES-SCLC who have completed 4 cycles of carboplatin and etoposide induction chemotherapy and at least 3 cycles of *atezolizumab* as their first-line therapy for extensive-stage disease and have *responded* (*CR or PR*) or have SD are eligible for the maintenance arm of the study.

Dose Escalation (Arms A and B) and Dose Expansion

- Signed Informed Consent Form
- Age \geq 18 years at time of signing Informed Consent Form
- Ability to comply with the study protocol, in the investigator's judgment
- ECOG performance status of 0 or 1
- Patients must be able to swallow pills
- Histologically or cytologically confirmed diagnosis of ES-SCLC per the Veterans Administration Lung Study Group (VALG) staging system
- Patients who received prior chemoradiotherapy for limited-stage SCLC must have been treated with curative intent and experienced a treatment-free interval of at least 6 months since last chemotherapy, radiotherapy, or chemoradiotherapy cycle prior to diagnosis of ES-SCLC
- Patients with a history of treated CNS metastases that are currently asymptomatic are eligible, provided they meet all of the following criteria:
 - Only supratentorial and cerebellar metastases allowed (i.e., no metastases to midbrain, pons, medulla or spinal cord)
 - No ongoing requirement for corticosteroids as therapy for CNS disease
 - No evidence of interim progression between the completion of CNS-directed therapy and enrollment
 - Patients with new asymptomatic CNS metastases detected at the screening scan must receive radiation therapy and/or surgery for CNS metastases.

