 Following treatment, these patients may then be eligible without the need for an additional brain scan prior to enrollment, if all other criteria are met.
- Measurable disease, as defined by RECIST v1.1. Baseline measurements and evaluation of all sites of disease must be obtained ≤ 4 weeks prior to enrollment.
 - Previously irradiated lesions can only be considered as measurable disease if disease progression has been unequivocally documented at that site since radiation and the previously irradiated lesion is not the only site of disease.
- Eligible to receive a carboplatin-based chemotherapy regimen

- Adequate hematologic and end-organ function, defined by the following laboratory results obtained within 14 days prior to enrollment:
 - ANC \geq 1500 cells/ μ L (without granulocyte-colony stimulating factor support within 7 days prior to Cycle 1, Day 1)
 - Lymphocyte count \geq 500 cells/ μ L
 - Platelet count \geq 100,000 cells/µL without transfusion
 - Hemoglobin \geq 9.0 g/dL

Patients may be transfused to meet this criterion.

– INR or aPTT $\leq 1.5 \times ULN$

This applies only to patients who are not receiving the rapeutic anticoagulation; patients receiving the rapeutic anticoagulation should be on a stable dose and with INR \leq 3.5 \times ULN.

- AST (SGOT), ALT (SGPT), and alkaline phosphatase $\leq 2.5 \times ULN$ with the following exceptions:

Patients with documented liver metastases: AST and/or ALT \leq 5 \times ULN

Patients with documented bone or liver metastases: alkaline phosphatase $\leq 5 \times ULN$

- Serum total bilirubin $\leq 1.5 \times ULN$

Patients with known Gilbert disease who have serum bilirubin level \leq 3 \times ULN may be enrolled.

- Albumin $\geq 25 \text{ g/L} (2.5 \text{ g/dL})$
- Creatinine clearance (CRCL) ≥ 50 mL/min calculated with the use of the 24hour CRCL or modified Cockcroft-Gault equation (i.e., estimation of creatinine clearance rate [eCCr]) with the use of ideal body mass (IBM) instead of mass:

 $eCCr = (140-age) \times (weight in kg) \times (0.85 if female)$ 72 × (serum creatinine in mg/dL)

Or, if serum creatinine is in μ mol/L:

eCCr = $(140 - age) \times IBM$ (kg) $\times (1.04$ if female) serum creatinine (μ mol/L)

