4.1.2 Exclusion Criteria

- Use of non–protocol-specified anti-cancer therapies or other combination partners with carboplatin/etoposide during induction
- Symptomatic or actively progressing CNS metastases

Note: Asymptomatic patients with treated (i.e., local CNS-directed therapy) or untreated CNS lesions are eligible, provided that all of the following criteria are met:

- Measurable disease, per RECIST v1.1, must be present outside the CNS.
- The patient has no history of intracranial hemorrhage or spinal cord hemorrhage from CNS disease.
- Metastases are limited to the cerebellum or the supratentorial region (i.e., no metastases to the midbrain, pons, medulla, or spinal cord).
- The patient has no symptoms caused by CNS disease (i.e., no headache, nausea, vomiting, convulsion, paralysis, etc.).
- The patient has no ongoing requirement for anticonvulsants for CNS disease.
- The patient has no ongoing requirement for dexamethasone/corticosteroids for CNS disease (previously untreated patients must also not have any history of requiring or receiving dexamethasone/corticosteroids for CNS disease).
- For patients with previously treated CNS metastases, there is no evidence of interim CNS progression between the completion of CNS-directed therapy and enrollment.
- For previously untreated patients, there is no evidence of brain edema related to CNS disease (e.g., vasogenic edema).
- For previously untreated patients, a brain magnetic resonance imaging (MRI) scan with contrast is required at screening and is the preferred modality for all subsequent scheduled follow-up tumor assessments.

Note: Computed tomography (CT) scan with contrast may be acceptable for all subsequent scheduled follow-up tumor assessments if the following criteria are met.

 Both brain MRI and CT scan with contrast must be performed at screening to assess untreated CNS disease. The CT scan with contrast can be used to reliably evaluate lesions identified on the screening MRI with contrast.

If CT scan with contrast cannot be used to reliably evaluate lesions identified on the screening MRI with contrast, then MRI scan with contrast must be used at all subsequent scheduled follow-up tumor assessments.

The same modality must be used at every tumor assessment.

• Pregnant or breastfeeding, or intending to become pregnant during the study

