Screening and subsequent tumor assessments must include CT scans (with oral and/or IV contrast unless contraindicated). A CT scan of the pelvis is required at screening and as clinically indicated or as per local standard-of-care at subsequent response evaluations. MRI scans with contrast of the chest, abdomen, and pelvis with a non-contrast CT scan of the chest may be used in patients for whom CT scans with contrast are contraindicated (i.e., patients with contrast allergy or impaired renal clearance).

A CT (with contrast) or MRI scan with contrast (if CT contrast is contraindicated) of the head must be done at screening to evaluate CNS metastasis in all patients. If CT with contrast is performed and the presence of brain metastases is considered equivocal, an MRI scan of the brain is required to confirm or refute the diagnosis of CNS metastases at baseline.

Patients with active or untreated symptomatic CNS metastases are not eligible for the study (see Section 4.1.2). Patients with untreated asymptomatic CNS metastasis at screening may be eligible. For untreated patients, brain MRI scan with contrast at screening is required, and need to meet all eligibility criteria as specified in Section 4.1.2.

If a CT scan for tumor assessment is performed in a positron emission tomography (PET)/CT scanner, the CT acquisition must be consistent with the standards for a full contrast diagnostic CT scan.

Venetoclax—F. Hoffmann-La Roche Ltd Page 93 of 214 Protocol GO41864, Version 2 Further investigations such as bone scans and CT scans of the neck should also be performed if clinically indicated. At the investigator's discretion, other methods of assessment of measurable disease as per RECIST v1.1 may be used.

Tumor assessments performed as standard-of-care prior to obtaining informed consent and within 28 days of Cycle 1, Day 1 may be used rather than repeating tests. All known sites of disease, including measurable and/or non-measurable disease, must be documented at screening and re-assessed at each subsequent tumor evaluation.

At subsequent (post-screening) tumor assessments, patients with a history of treated brain metastases at screening are not required to undergo brain scans unless clinically indicated (e.g., in patients with neurological symptoms). The same radiographic procedure used to assess disease sites at screening should be used throughout the study (e.g., the same contrast protocol for CT scans).

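### For never-treated, asymptomatic CNS metastases first seen on the screening scan, Section 4.1.1 read literally requires radiation or surgery before enrollment, while Sections 4.1.2 and 4.5.5 admit them untreated

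*Combined protocol and SAP*

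**What the plan says.** Section 4.1.1 has a bullet that opens: "Patients with a history of treated CNS metastases that are currently asymptomatic are eligible, provided they meet all of the following criteria". Four sub-bullets follow, on lesion location, corticosteroid need, interim progression, and new lesions. The fourth reads: "Patients with new asymptomatic CNS metastases detected at the screening scan must receive radiation therapy and/or surgery for CNS metastases". It continues that, after treatment, such patients may be "eligible without the need for an additional brain scan prior to enrollment, if all other criteria are met". The inclusion criteria in the synopsis have the same text and nesting.

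Section 4.1.2 excludes symptomatic or actively progressing CNS metastases, then adds a note: "Asymptomatic patients with treated (i.e., local CNS-directed therapy) or untreated CNS lesions are eligible, provided that all of the following criteria are met". Some of the listed conditions apply to all patients with CNS lesions, for example: "The patient has no history of intracranial hemorrhage or spinal cord hemorrhage from CNS disease". Others apply only to treated patients, such as: "For patients with previously treated CNS metastases, there is no evidence of interim CNS progression between the completion of CNS-directed therapy and enrollment". Others apply only to previously untreated patients: no brain edema, no history of steroid use for CNS disease, and a contrast brain MRI at screening. The synopsis repeats the note.

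Section 4.5.5 states: "Patients with untreated asymptomatic CNS metastasis at screening may be eligible". It adds that untreated patients "need to meet all eligibility criteria as specified in Section 4.1.2", and it requires untreated CNS disease to be recorded at screening and at later scheduled tumor assessments.

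Under Section 4.5.1, all eligibility criteria are to be confirmed before enrollment. Section 9.2 rules out requests to waive eligibility criteria.

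**The concern.** Section 4.5.5 requires head imaging of every patient at screening, so the screening scan is an ordinary way for an asymptomatic brain lesion to come to light. For a patient never treated for CNS disease, the site then has two instructions. The inclusion list says to treat the lesion first. The note in the exclusion list says the lesion may stay untreated if the conditions are met.

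At stake is whether the patient has brain radiation or surgery before study treatment, and whether the patient may enroll at all without it. It also affects reporting: Section 6.2 plans a summary of major deviations from the inclusion and exclusion criteria, and the same untreated enrollment could count as a deviation under one rule and as compliant under the other. Section 9.5 plans approximately 10–12 sites, so the question may be answered more than once and in different ways.

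**Working it through.** No figure in the plan is involved, so the check sets the rules side by side and applies them to cases.

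| Case (asymptomatic throughout) | Section 4.1.1, read literally | Sections 4.1.2 and 4.5.5 | Conflict? |
|---|---|---|---|
| Lesion known before screening, never treated | New-lesion sentence does not apply | May enroll untreated if conditions are met | No |
| No prior CNS therapy; lesion first seen at screening; left untreated | Not eligible until treated | May enroll if conditions are met | **Yes** |
| Same patient, lesion then irradiated or resected | Eligible if all other criteria are met | Eligible if the conditions for treated lesions are met | No |
| Previously treated CNS disease, new lesion at screening | Must be treated, but the preceding sub-bullet bars interim progression | Interim CNS progression bars the patient | Separate problem (below) |

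1. Take the second row: a new supratentorial lesion with no edema, no hemorrhage, no steroid or anticonvulsant use, a contrast MRI done at screening, and measurable disease outside the CNS. Every 4.1.2 condition is met. The 4.1.1 sentence is not, because no radiation or surgery has been given.
2. Section 4.5.1 requires all criteria to be met. The 4.1.2 note qualifies an exclusion criterion and does not say that it lifts an inclusion requirement. Read literally, the patient is therefore barred by 4.1.1 although 4.1.2 and 4.5.5 describe the patient as potentially eligible.
3. Section 9.2 closes the waiver route.
4. No section limits the untreated provisions to lesions known before screening. None limits the 4.1.1 sentence to patients with earlier CNS treatment, except by its position on the page.

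Reach of the eligibility list: Section 4.1 plans 18–42 escalation patients plus an estimated 20 in expansion, so 18 + 20 = 38 to 42 + 20 = 62 patients. That is everyone the list covers, not the number affected. The documents give no rate for newly detected, asymptomatic CNS lesions.

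**The case against.** The strongest objection is that the new-lesion sentence belongs to its parent bullet. On that reading it concerns only previously treated patients; never-treated patients use 4.1.2, as 4.5.5 directs, and nothing conflicts. This carries weight: the nesting and the cross-reference are the best evidence that the untreated route was intended. They do not settle the matter. The sentence is worded for any new lesion on the screening scan. The narrow reading also fits poorly with the sub-bullet just before it, which bars interim progression. Appendix 5 treats a new malignant lesion as progression, so a previously treated patient with a new lesion would ordinarily fail that condition.

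A second objection runs the other way: since all criteria are cumulative, the stricter 4.1.1 rule simply prevails, and the untreated provisions serve lesions known before screening. That is a possible reading, and a site that treats the lesion and then meets every other criterion complies with both rules. But 4.5.5 speaks of lesions untreated at screening without excluding new ones. The two objections resolve the text in opposite directions, which is itself the difficulty.

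A reader might go further and infer that the protocol contradicts itself for all untreated CNS lesions. It does not: lesions known before screening but never treated fall only under 4.1.2. A reader might also infer a 28-day delay from the exclusion for recent major surgery. That needs surgery to be the chosen therapy and to count as major, a term the protocol does not define; no such interval is stated for radiation.

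**Conclusion.** The conflict stands for one group: asymptomatic patients with no prior CNS-directed therapy whose CNS metastases are first detected on the screening scan and left untreated. The context suggests that they were meant to be eligible under 4.1.2, but the literal requirement in 4.1.1 still bars them. Differing site decisions on brain therapy, eligibility and deviations are a possibility the text leaves open; the documents do not show that they will occur, and the sponsor could clarify the point for sites.

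The number of patients concerned is unknown and may be zero. A reader might infer bias in ORR, PFS or DOR; the documents give no basis for estimating any such effect, and none is claimed. Sample size and dose-finding rules are not touched. The conclusion assumes only that inclusion and exclusion criteria apply together, as Section 4.5.1 requires. The point is worth correcting because it decides whether a patient has brain radiation or surgery before enrolling, and the correction is small.

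**What to change.** Take the new-lesion sub-bullet out of the bullet on treated CNS metastases, in Section 4.1.1 and in the synopsis, and replace it with a separate inclusion bullet along these lines:

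> Patients with no prior CNS-directed therapy whose asymptomatic CNS metastases are newly detected at the screening scan may be enrolled untreated if they meet all Section 4.1.2 conditions for untreated lesions, with brain imaging per Section 4.5.5. If they instead receive radiation and/or surgery, they may be enrolled without a further brain scan, provided all other criteria, including the Section 4.1.2 conditions for treated lesions, are met. Patients with previously treated CNS metastases and a new lesion at screening are subject to the no-interim-progression condition.

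The last sentence is needed so that the previously treated group is not left between two rules.

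This wording follows the intent that the context suggests. If the sponsor means treatment to be mandatory, keep the requirement and instead exclude lesions newly detected at screening from the untreated provisions in Section 4.1.2, Section 4.5.5 and the synopsis.

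Either option is a set of wording edits, but it changes eligibility text. It therefore goes through a protocol amendment with IRB/EC approval and, where locally required, regulatory approval (Section 9.7). The choice also determines whether these patients have brain imaging at scheduled tumor assessments, as 4.5.5 requires for untreated lesions. Sample size and analysis methods do not change.

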Patients with documented bone or liver metastases: alkaline phosphatase \leq 5 \times ULN

- Serum total bilirubin $\leq 1.5 \times ULN$

Patients with known Gilbert disease who have serum bilirubin level \leq 3 \times ULN may be enrolled.

- Albumin ≥ 25 g/L (2.5 g/dL)

 Creatinine clearance (CRCL) ≥ 50 mL/min calculated with the use of the 24-hour CRCL or modified Cockcroft-Gault equation (i.e., estimation of creatinine clearance rate [eCCr]) with the use of ideal body mass (IBM) instead of mass:

> eCCr = $(140 - age) \times (weight in kg) \times (0.85 \text{ if female})$ 72 × (serum creatinine in mg/dL)

Or, if serum creatinine is in μ mol/L:

 $eCCr = (140 - age) \times IBM (kg) \times (1.04 \text{ if female})$

serum creatinine (µ mol/L)

- Patients must submit a pre-treatment tumor tissue sample. Any available tumor tissue sample can be submitted (fresh, paraffin-embedded tissue block, or serial cut slides [15 preferred]). The tissue sample should be submitted before or within 4 weeks after enrollment; however, patients may be enrolled into the study before the pre-treatment tumor tissue sample is submitted. If tissue is not available, approval from the Medical Monitor is required before enrolling.
- Patients must submit a blood sample for exploratory biomarker research before treatment, on-study, and following progression of disease.
- For women of childbearing potential: agreement to remain abstinent (refrain from heterosexual intercourse) or use non-hormonal contraceptive methods that result in a failure rate of < 1% per year during the treatment period and for at least 30 days after the final dose of venetoclax, 5 months after the final dose of atezolizumab, or 6 months after the final dose of carboplatin or etoposide, whichever is longer. Women must refrain from donating eggs during this same period.

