9.5 ADMINISTRATIVE STRUCTURE

This trial will be sponsored and managed by F. Hoffmann-La Roche Ltd. The Sponsor will provide clinical operations management, data management, and medical monitoring.

Approximately 10–12 sites globally will participate to enroll approximately 62 patients. Screening and enrollment will occur through an IxRS.

Central facilities will be used for certain study assessments throughout the study (e.g., specified laboratory tests, biomarker analyses, and PK analyses), as specified in Section 4.5.7. Accredited local laboratories will be used for routine monitoring; local laboratory ranges will be collected.

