Appendix 9: Guidelines for Defining Tumor Lysis Syndrome (cont.)

Table 2 Howard Definition of Clinical Tumor Lysis Syndrome

The presence of laboratory TLS and one or more of the following criteria:

Creatinine^a: An increase in serum creatinine level of 0.3 mg/dL (26.5 μ mol/L); a single value >1.5 times the ULN of the age appropriate normal range if no baseline creatinine measurement is available; or the presence of oliguria, defined as average urine output of <0.5 mL/kg/hour for 6 hours

Cardiac dysrhythmia or sudden death probably or definitely caused by hyperkalemia

Cardiac dysrhythmia, sudden death, seizure, neuromuscular irritability (tetany, paresthesias, muscle twitching, carpopedal spasm, Trousseau's sign, Chvostek's sign, layngospasm or bronchospasm), hypotension, or heart failure probably or definitely caused by hypocalcemia^b

TLS=tumor lysis syndrome; ULN=upper limit of normal.

- ^a Acute kidney injury is defined as an increase in the creatinine level of ≥0.3 mg/dL (26.5 umol/L) or a period of oliguria lasting ≥6 hours. By definition, if acute kidney injury is present, the patient has clinical TLS.
- ^b Not directly attributable to a therapeutic agent.

REFERENCE

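### The µmol/L creatinine-clearance formula omits the factor for men (about 1.23), so the 50 mL/min entry limit acts as about 61 mL/min for them

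*Combined protocol and SAP*

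**What the plan says.** Section 4.1.1 sets the renal criterion as "Creatinine clearance (CRCL) ≥ 50 mL/min calculated with the use of the 24hour CRCL or modified Cockcroft-Gault equation". A measured 24-hour clearance is therefore allowed, and the estimate is the alternative. The lead-in tells sites to use ideal body mass (IBM) in the estimate.

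Two formulas follow, offered as alternatives by unit of serum creatinine:

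- **mg/dL:** (140 − age) × mass, with the terms "weight in kg) \times (0.85 if female", divided by "72 × (serum creatinine in mg/dL".
- **µmol/L:** (140 − age) × IBM, with a factor of 1.04 for women, divided by serum creatinine: "1.04$ if female) serum creatinine".

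The Synopsis repeats the µmol/L version with the same single sex term: "IBM (kg) \times (1.04 \text{ if female". Stray symbols inside these quotes come from reading the PDF and are not in the plan. Neither place prints a factor for men in the µmol/L version.

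Appendix 9, in the clinical tumor lysis table, supplies the protocol's own creatinine conversion: "0.3 mg/dL (26.5 umol/L) or a period of oliguria lasting".

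**The concern.** Two formulas that differ only in the unit of creatinine must give the same clearance for the same patient. Here they agree for women and disagree for men.

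The sex adjustment also changes direction. In the mg/dL version a woman scores 15% below a man with the same values; in the µmol/L version, read as printed, she scores 4% above him. Both cannot be right.

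The result feeds a fixed inclusion limit, so a man's eligibility could depend on his laboratory's reporting unit. Creatinine is measured at local laboratories (Sections 4.5.7 and 9.5), and Section 9.5 says that 10 to 12 "sites globally will participate to enroll approximately 62 patients". Section 9.2 does not allow waivers of eligibility criteria. A site that follows the text fails the man, and a site that supplies the missing factor itself departs from the text. What is at stake is the loss of eligible men from a small study.

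**Working it through.** **Inputs**

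- Threshold: 50 mL/min (Section 4.1.1).
- mg/dL formula: divisor 72 × creatinine; factor 0.85 for women, 1 for men (Section 4.1.1).
- µmol/L formula: factor 1.04 for women, none printed for men (Section 4.1.1 and Synopsis).
- Conversion: 0.3 mg/dL = 26.5 µmol/L (Appendix 9), so c = 26.5 / 0.3 = 88.33 µmol/L per mg/dL.

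**Step 1: reproduce the printed female factor.** Replacing creatinine in mg/dL by creatinine in µmol/L divided by c turns the mg/dL formula into one with multiplier 0.85 × c / 72 for women:

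0.85 × 88.33 / 72 = 1.043, printed as 1.04.

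The match shows that the µmol/L line was meant as a straight unit conversion.

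**Step 2: derive the male factor.** The same conversion without 0.85 gives

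88.33 / 72 = 1.227, about 1.23.

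This factor is absent, so a literal reading uses 1.00.

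**Step 3: size of the error, with the same body mass in both formulas.**

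- Ratio of the printed to the converted estimate for men: 1 / 1.227 = 0.815, an understatement of 18.5%.
- Effective male limit on the mg/dL formula: 50 × 1.227 = 61.3 mL/min.
- Effective female limit: 50 × 1.043 / 1.04 = 50.1 mL/min, essentially unchanged.
- With the usual conversion of 88.4 instead of 88.33, the male factor is 1.228 and the limit 61.4 mL/min.

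**Step 4: an example.** Take a patient aged 70 with a mass of 70 kg, so (140 − 70) × 70 = 4900, and creatinine 1.2 mg/dL = 106 µmol/L.

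| | mg/dL formula | µmol/L formula as printed |
|---|---|---|
| Man | 4900 / (72 × 1.2) = 56.7 | 4900 / 106 = 46.2 |
| Woman | 56.7 × 0.85 = 48.2 | 4900 × 1.04 / 106 = 48.1 |

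The man passes by one formula and fails by the other. The woman gets the same answer from both.

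The highest creatinine at which this man is eligible is 4900 / (72 × 50) = 1.36 mg/dL (120 µmol/L) by the first formula. By the second it is 4900 / 50 = 98 µmol/L (98 / 88.33 = 1.11 mg/dL).

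**Step 5: which line is the outlier.** Section 4.3.2.4 prints Cockcroft-Gault again for carboplatin dosing, with the divisor 72 × creatinine and 0.85 for women. That agrees with the mg/dL version in Section 4.1.1, so the µmol/L line is the one out of step.

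**The case against.** The arithmetic is not in dispute. The case on the other side concerns reach and reading.

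- **Reach.** Harm needs a man with a clearance of about 50 to 61 mL/min, at a site that reports µmol/L, uses the estimate and applies the line literally. The documents give neither the number of such sites nor the number of such men. A 24-hour measurement avoids both formulas, Section 3.1.1 allows one re-screening, and the complete mg/dL formula stands directly above the faulty line. All of this stands. It limits the number affected and makes some losses recoverable, but the rule remains wrong.
- **Direction.** The error is conservative: it admits nobody below 50 mL/min, does not enter the carboplatin dose, and changes no endpoint, sample size or precision figure. This also stands, and it is why the point is about eligibility and not safety.
- **Selective literalness.** The mg/dL line prints weight and the µmol/L line prints ideal body mass, so a wholly literal comparison multiplies 61.3 by actual over ideal mass. As an illustration with an ideal mass of 70 kg, that gives 61.3 × 60/70 = 52.6 at an actual 60 kg and 61.3 × 85/70 = 74.5 at 85 kg. However, the lead-in prescribes ideal body mass for the estimate, so equal mass is the protocol's stated rule and 61 is the fair figure.
- **Layout.** The formula blocks lost their fraction bars when read from the PDF, so a lost term is conceivable. Both copies carry a complete female term and no male term, which makes that unlikely. A look at the source page would settle it.

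**Conclusion.** The concern holds: the µmol/L formula is wrong as written for men. It omits a factor of about 1.23, understates male clearance by about 18.5%, and moves the effective male limit from 50 to about 61 mL/min. The female factor is correct.

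The figures rest on the Appendix 9 conversion, on the same (ideal) body mass in both formulas, and on a literal reading of the printed line. The number of patients affected cannot be estimated from the documents. The consequence is possible wrongful exclusion of men who meet the protocol's own mg/dL criterion, with no added safety exposure. It should be corrected because it feeds a fixed entry rule that sites may not waive.

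**What to change.** In Section 4.1.1 and in the Synopsis, print the µmol/L formula with both sex factors:

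eCCr = (140 − age) × IBM (kg) × (1.23 if male, 1.04 if female) / serum creatinine (µmol/L).

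Keep the 50 mL/min threshold and the 24-hour alternative as they are. In the same edit, reconcile the mass term in the mg/dL formula, which prints weight, with the lead-in, which specifies ideal body mass. That is a separate wording point and contributes nothing to the 61 mL/min figure.

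The cost is one formula line in two places, plus the wording fix. It adds no procedures and changes no clinical rule; it restores the equivalence between units that the protocol already intends.
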